13.7 Exploratory Analyses

Exploratory analyses will focus on two areas. First, the fit of the proposed model will be assessed and development of the most parsimonious model will be undertaken. Second, subgroup analyses will be performed. For example, we will explore whether abstinence rates differ across race, ethnicity, or gender, as well as whether they are effect modifiers for the relationship between NAC and abstinence.

13.8 Demographic and Baseline Characteristics

Baseline demographic and clinical variables will be summarized for each arm of the study. Descriptive summaries of the distribution of continuous baseline variables will be presented with percentiles (median, 25th and 75th percentiles), and with means and standard deviations. Categorical variables will be summarized in terms of frequencies and percentages. Since randomization is expected to produce balance at baseline between the two arms of the trial, statistical comparisons of treatment groups with respect to baseline characteristics will be more informal. In case differences between treatment arms are suspected, statistical testing will be

performed. For comparisons of treatment groups with respect to continuous baseline variables we will use the two-sample Wilcoxon test. Group comparisons with respect to discrete baseline variables will use the chi-square test or Fisher's Exact Test as appropriate.

13.9 Safety Analysis

Adverse events (AEs), including serious adverse events (SAEs), will be summarized by system organ class and preferred term using MedDRATM (The Medical Dictionary for Regulatory Activities). Adverse events will be presented in two ways: (1) the number and proportion of participants experiencing at least one incidence of each event will be presented overall and by treatment group; and (2) a table displaying the total number of each event will be given overall and by treatment group. Listings of serious adverse events will be given, sorted by treatment, system organ class, and preferred term. Detail in these listings will include severity, relationship to study drug, and action taken as available. Treatment arm differences will be monitored by the DSMB.

14.0 REGULATORY COMPLIANCE AND SAFETY MONITORING

14.1 Regulatory Compliance

This study will be conducted in accordance with the current version of the protocol, in accordance with the ethical principles outlined in the Declaration of Helsinki, International Conference on Harmonization Good Clinical Practice (GCP) Guidelines, and all other applicable regulatory requirements. An Operations Manual will be provided as a reference guide and study quality assurance tool.

14.2 Statement of Compliance

This trial will be conducted in compliance with the appropriate protocol, current Good Clinical Practice (GCP), the principles of the Declaration of Helsinki, and all other applicable regulatory requirements. Participating sites must obtain written approval of the study protocol, consent form, other supporting documents, and any advertising for participant recruitment from their local Institutional Review Board (IRB) in order to participate in the study. Prior to study initiation, the protocol and the informed consent documents will be reviewed and approved by an appropriate Ethics Review Committee (ERC) or IRB. Any amendments to the protocol or consent materials must be approved before they are implemented. Annual progress reports and local Serious Adverse Event (SAE) reports will be submitted to each IRB, according to its usual procedures.

14.3 Confidentiality

By signing the protocol signature page the investigator affirms that information furnished to the investigator by NIDA will be maintained in confidence and such information will be divulged to the IRB, Ethical Review Committee, or similar expert committee; affiliated institution; and employees only under an appropriate understanding of confidentiality with such board or committee, affiliated institution and employees. The Lead Investigator will obtain a federal Certificate of Confidentiality (CoC), protecting participants against disclosure of sensitive information (e.g., drug use), and will distribute it to all sites when received. The federal office that issues the CoC will be advised of changes in the CoC application information. Participating sites will be notified if CoC revision is necessary.

Participant records will be held confidential by the use of study codes for identifying participants on CRFs, secure storage of any documents that have participant identifiers, and secure computing procedures for entering and transferring electronic data.

A description of this clinical trial will be available on http://www.ClinicalTrials.gov, as required by U.S. Law. At most, the web site will include a summary of the results. Additionally, data from this study will be available to researchers on another website, http://datashare.nida.nih.gov/, after the study is complete and the data analyzed. These websites will not include information that can identify participants, and may be viewed at any time.

14.3.1 Health Insurance Portability Accountability Act (HIPAA)

Study sites may be required by their institutions to obtain authorization from participants for use of protected health information. Sites will be responsible for communicating with their IRBs or Privacy Boards and obtaining the appropriate approvals or waivers to be in regulatory compliance.

14.3.2 Investigator Assurances

Each site must file (or have previously filed) a Federal Wide Assurance (FWA) with the DHHS Office for Human Research Protection setting forth the commitment of the organization to establish appropriate policies and procedures for the protection of human research subjects, with documentation sent to NIDA or its designee. Research covered by these regulations cannot proceed in any manner prior to NIDA receipt of certification that the research has been reviewed and approved by the IRB provided for in the assurance (45 CFR 46.103(b) and (f)). Prior to initiating the study, the Principal Investigator at each study site will sign a protocol signature page, providing assurances that the study will be performed according to the standards stipulated therein.

14.3.3 Financial Disclosure

All investigators will comply with the requirements of 42 CFR Part 50, Subpart F to ensure that the design, conduct, and reporting of the research will not be biased by any conflicting financial interest. Everyone with decision-making responsibilities regarding the protocol must comply with their institution's policy regarding conflict of interest.

14.3.4 Inclusion of Women and Minorities

A diverse group of study sites will be involved so that these sites can attract a diverse study population. If difficulty is encountered in recruiting an adequate number of women and/or minorities, the difficulties involved in recruitment will be discussed in national conference calls and/or face-to-face meetings, encouraging such strategies as linkages with medical sites and or treatment programs that serve a large number of women or minorities, advertising in newspapers or radio stations with a high female or minority readership/listening audience, etc.

14.3.5 IND Requirements

An IND application will be submitted to the FDA for this study. Any subsequent amendments to this clinical trial submitted to the FDA for review will reflect awareness of and compliance with U.S Code of Federal Regulations 45 CFR 46 and its subparts, as well as the International Conference on Harmonization Good Clinical Practice (ICH E6). This IND study will also be conducted in accordance with all applicable FDA regulations and will comply with all applicable laws and regulations at clinical research sites.

14.3.6 Regulatory Files

The regulatory files should contain all required regulatory documents, study-specific documents, and important communications. Regulatory files will be checked at each participating site for the regulatory documents compliance prior to study initiation, throughout the study, and at study closure.

14.3.7 Records Retention and Requirements

Research records for all study participants (e.g., case report forms, source documents, signed consent forms, and regulatory files) are to be maintained by the investigator in a secure location for a minimum of 3 years after the study is completed and closed. These records are also to be maintained in compliance with local IRB, State and Federal requirements, whichever is longest. The Sponsor and Lead Investigator must be notified in writing and acknowledgment must be received by the site prior to the destruction or relocation of research records.

14.3.8 Audits

The Sponsor has an obligation to ensure that this trial is conducted according to good research practice guidelines and may perform quality assurance audits for protocol compliance. The Lead Investigator and authorized staff from the Southern Consortium Node; the National Institute on Drug Abuse Clinical Trials Network (NIDA CTN, the study Sponsor); NIDA's contracted agents, monitors or auditors; and other agencies such as the Department of Health and Human Services, the Office for Human Research Protection and the sites' Institutional Review Board may inspect research records for verification of data, compliance with federal guidelines on human participant research, and to assess participant safety.

14.3.9 Reporting to Sponsor

The site Principal Investigator agrees to submit accurate, complete, legible, and timely reports to the Sponsor, as required. These include, but are not limited to, reports of any changes that significantly affect the conduct or outcome of the trial or increase risk to study participants. Adverse Event reporting and Serious Adverse Event reporting will occur as previously described. At the completion of the trial, the Lead Investigator will provide a final report to the Sponsor.

14.3.10 Informed Consent

The informed consent form is a means of providing information regarding the trial to a prospective participant and allows for an informed decision about participation in the study. Each study site must have the study informed consent approved by their IRB(s). A copy of the IRB-approved consent, along with the IRB study approval, must be sent to the Clinical Coordinating Center (CCC) and the Lead Node prior to the site initiation visit. Every study participant is required to sign a valid, IRB-approved current version of the study informed consent form prior to the initiation of any study related procedures. The site must maintain the original signed informed consent for every participant in a locked, secure location that is in compliance with IRB and institutional policies and that is accessible to the study monitors.

Prior to signing the informed consent form, research staff knowledgeable about the study will explain the study to the potential participant and provide him/her with a copy of the consent to read. If the potential participant is interested in participating in the study, a researcher who is authorized to obtain informed consent by the PI and (if applicable) by the IRB, will review each section of the informed consent form in detail, answer any of the participant's questions, and determine if the participant comprehends the information provided by administering the comprehension tool. The participant will document agreement to participate by signing and dating the consent document. The person obtaining consent and a witness, if required by the local IRB(s), will also sign and date the consent document. The consent must be properly executed and complete to be valid. It is strongly recommended that another research staff member review the consent after it is signed to ensure that the consent is properly executed and complete. Persons delegated by the PI to obtain informed consent must be listed on the Site Staff Delegation of Responsibilities and Signature Log and must be approved by the IRB, if required. All persons obtaining consent must have completed appropriate training. A copy of the informed consent document will be provided to the participant, and this action will be noted in the participant's record.

In order to ensure that potential study participants understand the research study, a comprehension "quiz" (referred to as a comprehension tool) will be administered to potential participants prior to the informed consent being signed. Those who cannot successfully answer quiz items will have the study re-explained by research staff with a focus on aspects they did not understand. Those who demonstrate understanding of the study and voluntarily agree to

participate will be asked to sign the Informed Consent Form. The content of the quiz may be modified per local IRB requirements.

The informed consent form must be updated or revised whenever important new safety information is available, or whenever the protocol is amended in a way that may affect a participant's participation in the trial. All participants affected by the change will be re-consented (based on local IRB policy). The participants will be informed that their participation is voluntary and they may withdraw from the study at any time, for any reason without penalty.

Individuals who refuse to participate or who withdraw from the study will be treated without prejudice. Study sites will be responsible for maintaining signed consent forms as source documents for quality assurance review and regulatory compliance.

14.3.11 Clinical Monitoring

The monitoring of the study site will be conducted on a regular basis using a combination of NIDA-contracted monitors and RRTC (Regional Research and Training Center) site managers. Investigators will host periodic visits by NIDA contract monitors who will ensure all study procedures are conducted and that study data are generated, documented, and reported in compliance with the protocol, GCP, and applicable regulations. These monitors will audit, at mutually agreed upon times, regulatory documents, case report forms (CRFs), and corresponding source documents for each participant.

NIDA contract monitors will monitor study compliance and study procedures to assess compliance with the protocol, GCP, and applicable regulations. NIDA contract monitors will assess accurate submission of data and that data are in agreement with source documentation and will review regulatory/essential documents such as correspondence with the IRB. Areas of particular concern will be participant informed consent, protocol adherence, safety monitoring, IRB reviews and approvals, regulatory documents, participant records, study drug accountability, and principal investigator supervision and involvement in the trial. Reports will be prepared following the visit and forwarded to the site principal investigator, the lead investigator and NIDA.

Qualified node personnel (Node Protocol Managers and/or QA monitors) will provide site management for each site during the trial. This will take place as specified by the local protocol team, node PI or Lead Node, and will occur as often as needed to help prevent, detect, and correct problems at the study sites. Node staff will verify that study procedures are properly followed and that site staff are trained and able to conduct the protocol appropriately. If the node staff's review of study documentation indicates that additional training of study personnel is needed, node staff will undertake or arrange for that training. Details of the contract, node QA and data monitoring are found in the study Quality Assurance Monitoring Plan.

14.3.12 Study Documentation

Study documentation includes all case report forms, data correction forms, participant diaries, source documents, monitoring logs and appointment schedules, Sponsor-investigator correspondence, and signed protocol and amendments, Ethics Review Committee or Institutional Review Board correspondence and approved consent form and signed participant consent forms.

Source documents include all recordings of observations or notations of clinical activities and all reports and records necessary for the evaluation and reconstruction of the clinical research study. Whenever possible, the original recording of an observation should be retained as the source document; however, a photocopy is acceptable provided that it is a clear, legible, and exact duplication of the original document.

14.4 Safety Monitoring

14.4.1 Data and Safety Monitoring Board (DSMB)

NIDA has appointed a CCTN DSMB in accordance with NIH requirements to provide independent oversight of CTN trials. The DSMB will review the research protocol and plans and make recommendations to assure that subject safety, trial validity and data integrity are addressed appropriately. Throughout this trial, the DSMB will periodically assess at regularly scheduled meetings trial progress, factors that can affect study outcome, safety and outcome data, critical efficacy endpoints and factors or scientific discoveries external to the study that may have ethical considerations or may affect the risk benefit analysis of this study. After review of the trial data and other factors, the DSMB will make recommendations to NIDA on whether to continue, stop or modify the trial or an individual participant's participation in the trial.

14.4.2 Protocol Deviations Reporting and Management

Any departure from procedures and requirements outlined in the protocol will be classified as either a major or minor protocol deviation. The difference between a major and minor protocol deviation has to do with the seriousness of the event and the corrective action required. A minor protocol deviation is considered an action (or inaction) that by itself is not likely to affect the scientific soundness of the investigation or seriously affect the safety, rights, or welfare of a study participant. Major protocol deviations are departures that may compromise the participant safety, participant rights, inclusion/exclusion criteria or the integrity of study data and could be cause for corrective actions if not rectified or prevented from re-occurrence. Sites will be responsible for developing corrective action plans for both major and minor deviations as appropriate. Those corrective action plans may be reviewed/approved by the Lead Node and the CCC with overall approval by the site's IRB. All protocol deviations will be monitored at each site for (1) significance, (2) frequency, and (3) impact on the study objectives, to ensure that site performance does not compromise the integrity of the trial. The decision about whether a departure from the protocol will be designated as a major or minor protocol deviation will be made by the protocol's Lead Investigator in conjunction with the CCC and DSC.

All protocol deviations will be recorded in the Electronic Data Capture (EDC) system via the Protocol Deviations CRF. Additionally, each site is responsible for tracking and reporting protocol deviations to their IRB as required. Site staff should contact the DSC, CCC, and Lead Investigator immediately if an unqualified/ineligible participant is randomized into the study.

14.4.3 Adverse Events (AEs)

Each participating site will appoint a medical clinician (MD, PA, NP, etc.) for this study, who will review or provide consultation for each serious event as needed. These reviews will include an assessment of the severity and causality to the study drug or study procedures. The Medical Clinician will also provide advice for decisions to exclude, refer, or withdraw participants as required. In addition, NIDA will assign a Medical Monitor to this protocol to independently review the safety data, present it to the DSMB for periodic review, and provide site Principal Investigators a Safety Letter when necessary. The medical monitor will determine which safety events require expedited reporting to NIDA, the DSMB, and regulatory authorities. This will include all suspected adverse reactions that are serious and unexpected. The study staff will be trained to monitor for and report adverse events and serious events.

Each of the participating sites has established practices for managing medical and psychiatric emergencies, and the study staff will continue to utilize these procedures. Study medical clinicians at each site will be responsible for monitoring participants for possible clinical deterioration or other problems, and for implementing appropriate courses of action.

14.4.4 Definitions of Adverse Events and Serious Adverse Events

Standard definitions for adverse events and serious adverse events, their identification, characterization regarding severity and relationship to therapy and processing are described in Section 18.0 and Appendix A.

14.4.5 Reportable Adverse Events and Serious Adverse Events

Adverse Events

For the purpose of this study, the following AEs will not require reporting in the data system but will be captured in the source documentation as medically indicated:

- Grade 1 (mild) and unrelated adverse events
- This would typically include physical events such as headache, cold, etc., that were considered not reasonably associated with the use of the study drug/intervention.

Serious Adverse Events

For the purpose of this study, admission to a hospital or freestanding residential facility for drug detoxification will not be recorded as an SAE in the data system and will be reported to local IRBs per local IRB guidelines.

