18.0 APPENDIX A

Adverse Events - Definition of Adverse Event and Serious Adverse Event

Adverse Event: An adverse event (AE) is any untoward medical occurrence in humans, whether or not considered study drug/intervention related which occurs during the conduct of a clinical trial. (Any change from baseline in clinical status, ECGs, routine labs, x-rays, physical examinations, etc., that is considered clinically significant by the medical clinician are considered AEs.)

Suspected adverse reaction is any adverse event for which there is a reasonable possibility that the study drug/intervention caused the adverse event. A reasonable possibility implies that there is evidence that the study drug/intervention caused the event.

Adverse reaction is any adverse event caused by the study drug/intervention.

Serious Adverse Event (SAE): A serious adverse event (SAE) refers to all serious events including serious adverse events or serious suspected adverse reaction or serious adverse reaction as determined by the medical clinician or the sponsor is any event that results in any of the following outcomes:

- 1. Death: A death occurring during the study or which comes to the attention of the site research personnel during the protocol-defined follow-up after the completion of the study, whether or not considered treatment-related, must be reported.
- 2. Life-threatening AE (Life-threatening means that the study participant was, in the opinion of the medical clinician or sponsor, at immediate risk of death from the reaction as it occurred and required immediate intervention.)
- 3. Inpatient hospitalization or prolongation of existing hospitalization.
- 4. Persistent or significant incapacity or substantial disruption of the ability to conduct normal life functions.
- 5. Congenital abnormality or birth defect.
- Important medical event that may not result in one of the above outcomes, but may
 jeopardize the health of the study participant or require medical or surgical
 intervention to prevent one of the outcomes listed in the above definition of serious
 event.

Unexpected Adverse Event: Any adverse event, the specificity or severity of which is not consistent with the investigator brochure or the package insert. If neither is available then the protocol and consent are used to determine an unexpected adverse event.

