Site AE/SAE Monitoring: Protocol monitors as well as local node staff will review the study sites and respective study data on a regular basis and will promptly advise sites to report any previously unreported safety issues and ensure that the reportable safety-related events are being followed to resolution and reported appropriately by the research staff. Staff education, retraining or appropriate corrective action plan will be implemented at the participating site when unreported or unidentified reportable AEs or serious events are discovered, to ensure future identification and timely reporting by the site.

[figure not shown]
Sponsor's Role in Safety Management Procedures of AEs/SAEs: A NIDA-assigned Medical Monitor is responsible for reviewing all SAE reports. All reported SAEs will generate an e-mail notification to the Medical Monitor. All SAEs will be reviewed by the Medical Monitor in the study's data capture system and, if needed, additional information will be requested. The medical monitor will also report events to the sponsor and the Data and Safety Monitoring Board (DSMB). The DSMB will receive summary reports of all adverse events annually, at a minimum. The DSMB or the NIDA assigned Medical Monitor may also request additional and updated information. Details regarding specific adverse events, their treatment and resolution, will be summarized by the medical monitor in writing for review by the sponsor and DSMB. Subsequent review by the Medical Monitor, DSMB, FDA and ethics review committee or IRB, the sponsor, or relevant local regulatory authorities may also suspend further trial treatment at a site. The study sponsor, DSMB and FDA retain the authority to suspend additional enrollment and treatments for the entire study as applicable.

Reporting to the Data and Safety Monitoring Board: The DSMB will receive listing of reportable AEs and summary reports of all SAEs at a frequency requested by the DSMB, but at least annually. Furthermore, the DSMB will be informed of expedited reports of SAEs.

Regulatory Reporting for an IND study:

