19.2 Oversight of Clinical Responsibilities

A. Site Principal Investigator

Each participating site's PI is responsible for study oversight, including ensuring human research subject protection by designating appropriately qualified, trained research staff and medical clinicians to assess, report, and monitor adverse events.

Regarding safety and in accordance with FDA reporting requirements, all Adverse Events (AEs) occurring during the course of the clinical trial will be collected, documented, and reported by the investigator or sub-investigators according to the Protocol. The assessment of Adverse Events (medical and/or psychiatric) will commence at the time of participant consent and will continue through 30 days post last active treatment visit.

The occurrence of AEs and Serious Adverse Events (SAEs) will be assessed at each clinic visit during the study. Serious adverse events will be followed until resolved or considered stable, with reporting to the CCC Safety Monitor/Medical Monitor through the follow-up period.

Standard reporting, within 7 days of the site becoming aware of the event, is required for reportable AEs. Expedited reporting (within 24 hours of their occurrence and/or site's knowledge of the event) is required for reportable SAEs (including death and life-threatening events).

B. Medical Monitor/Safety Monitor

The NIDA Clinical Coordinating Center (CCC) Safety Monitor/Medical Monitor is responsible for reviewing all adverse events and serious adverse events reported. All SAEs will be reviewed at the time they are reported in the EDC. The Medical Monitor will also indicate concurrence or not with the details of the report provided by the site PI. Where further information is needed the Safety Monitor/Medical Monitor will discuss the event with the site. Reviews of SAEs will be conducted in the AdvantageEDC data system and will be a part of the safety database. All AEs are reviewed on a weekly basis to observe trends or unusual events.

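### The Section 13.9 adverse-event tables are worded to cover every event, but mild events judged unrelated need not be entered and detoxification admissions are not recorded as SAEs, so the tables can understate incidence

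*Protocol*

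**What the plan says.** - **Tables.** Protocol Section 13.9 states that "the number and proportion of participants experiencing at least one incidence of each event will be presented overall and by treatment group", and adds a second table with the total number of each event by arm. Neither is limited to reportable events.
- **AE definition.** Appendix A (Section 18.0) counts untoward occurrences "whether or not considered study drug/intervention related which occurs during the conduct of a clinical trial".
- **AE carve-out.** Section 14.4.5 states that "the following AEs will not require reporting in the data system but will be captured in the source documentation as medically indicated". The class is "Grade 1 (mild) and unrelated adverse events", with headache and colds as typical examples. Appendix A obliges sites to enter only reportable AEs and SAEs.
- **SAE carve-out.** Section 14.4.5 also states that "admission to a hospital or freestanding residential facility for drug detoxification will not be recorded as an SAE in the data system". It sends these admissions to local IRBs under local rules. The serious outcomes listed in Appendix A include "Inpatient hospitalization or prolongation of existing hospitalization", and no detoxification exception is given there.
- **DSMB.** In the paragraph on the sponsor's role, Appendix A says: "The DSMB will receive summary reports of all adverse events annually, at a minimum". The next paragraph, on reporting to the DSMB, offers a listing of reportable AEs and summaries of all SAEs.
- **Monitoring plan.** Appendix B (Section 19.2) says that "all Adverse Events (AEs) occurring during the course of the clinical trial will be collected, documented, and reported", but the sentence goes on to make this subject to the protocol.

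**The concern.** In a randomised, blinded trial, comparing the arms is how one learns whether an unanticipated event is caused by the drug. Section 14.4.5 lets one clinician's opinion on one case decide whether a mild event has to reach the data being compared. Two participants with the same mild headache can count differently in the Section 13.9 tables solely because one was judged related and the other was not.

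A reader of the final report, or a DSMB member, who takes these tables at their wording would read them as AE incidence. For mild events they would be the incidence of events that someone thought might be drug-related. Likewise, a hospital admission for detoxification, a sign of deterioration that matters in an addiction trial, would be absent from the SAE counts by arm, although the general definition in Appendix A would include it.

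This is a rule about data capture, so an analysis plan can relabel the tables but cannot restore what was not entered. Recovery from source documents is not assured, because capture there is required only when medically indicated.

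**Working it through.** The plan states no AE rate, so there is no figure to reproduce. The check has two parts.

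**1. Which events must reach the tables.** Sections 13.9 and 14.4.5 are set beside the definitions and data-entry duty in Appendix A.

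| Event | AE or SAE under Appendix A | Must it be entered? |
|---|---|---|
| Grade 2 or 3, any causality | AE | Yes |
| Grade 1, related | AE | Yes |
| Grade 1, unrelated | AE | No; source documents only as medically indicated |
| Detoxification admission that is an inpatient hospitalization | SAE | Not recorded as an SAE; no other data-system record is described |

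The causality judgement is a yes/no answer by the designated medical clinician (Appendix A). It decides entry only in the Grade 1 rows. The detoxification exclusion is by type of event.

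The two DSMB statements differ in scope: all adverse events in one, reportable AEs in the other. If the unreported events are not in the database, the first cannot be met from it.

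**2. Direction and scale, as an illustration only.** From the documents: about 300 randomised (Section 7.0), 1:1 (Section 9.4), so about 150 per arm. Assumed, not in the documents: a true incidence of 30% versus 20% for one event term, and a share *s* of affected participants whose every occurrence of that event is Grade 1, judged unrelated and not entered, equal in both arms.

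Recorded incidence = true incidence × (1 − *s*). For example, with *s* = 0.50: 30% × 0.50 = 15% and 20% × 0.50 = 10%.

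| *s* | Recorded, two arms | Difference (points) | Ratio | Power, two-sided 5%, 150 per arm |
|---|---|---|---|---|
| 0 | 30% vs 20% | 10 | 1.5 | 0.52 |
| 0.25 | 22.5% vs 15% | 7.5 | 1.5 | 0.38 |
| 0.50 | 15% vs 10% | 5 | 1.5 | 0.26 |
| 0.75 | 7.5% vs 5% | 2.5 | 1.5 | 0.14 |

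With equal true rates of 20%, the recorded rates fall to 15%, 10% and 5% in both arms and the difference stays at zero. A filter that acts equally in both arms therefore lowers incidence and shrinks absolute differences. It leaves the ratio alone and creates no imbalance. Section 13.9 describes no hypothesis test for AEs, so the power column only gauges how visible a real difference would be.

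**The case against.** The strongest reply is that selective capture is openly declared for this study, for a drug the protocol describes as having a long safety record, and that a specific rule overrides a general definition. Much of the document does work with reportable events: the data-entry duty and reporting timelines use that term, and the Appendix B sentence about all AEs defers to the protocol. That sentence is therefore not a clear contradiction. The statistical analysis plan, which is not shown, could also set the scope of the tables.

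Several limits on the point also stand:

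- A reader might infer that the excluded events can never enter the data system. The text waives a duty for mild unrelated AEs and bars recording detoxification admissions as SAEs; it does not forbid other entry.
- A reader might infer that SAE counts are filtered by causality. They are not.
- A reader might infer that the filter hides the expected effects of NAC. Section 14.4.6 describes these as generally mild and mostly gastrointestinal. Known effects are the likeliest to be judged possibly related and so to stay reportable; the exposure is to mild, unanticipated effects.
- A reader might infer bias between arms. Site staff are blind (Section 9.7.2), and nothing in the documents shows that the filter works differently by arm.
- Sleep, withdrawal, mood and anxiety, suicidality, weight and blood pressure are measured in all participants without a causality judgement, which gives partial cover.

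What the reply does not remove is that Section 13.9 is not limited to reportable events, that Appendix A describes the DSMB's AE material in two ways, and that the detoxification carve-out leaves no described means of counting those admissions by arm.

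**Conclusion.** The point holds as a mismatch between what the tables claim to show and what the database must contain. Followed as written, the Section 13.9 tables can understate the absolute incidence of mild AEs, can shrink absolute arm differences for mild, unanticipated effects, and leave detoxification admissions out of the SAE counts. The DSMB text is inconsistent about which AEs are summarised.

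The size cannot be determined: the documents give no AE rates, no share of mild events judged unrelated and no expected number of detoxification admissions, which may be few. The illustrative figures rest on assumed rates and an equal filter in both arms. The documents do not support a finding of biased arm comparisons or of a loss affecting moderate or severe events. The primary efficacy analysis, which rests on urine tests, is not touched. The correction should be made because it is cheap and settles what the safety tables can be said to show.

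**What to change.** 1. State in Section 13.9 and in the DSMB reporting text of Appendix A that the tables and reports cover reportable AEs only. Name both exclusions, and do not present the results as overall AE incidence. This costs wording only.
2. Enter detoxification admissions in the data system with a flag, so that they can be tabulated by arm. Expedited handling can stay as it is. This costs one data field and its completion.
3. Reconcile Section 13.9, Section 14.4.5, the Appendix A definitions and the two DSMB statements, so that one scope applies throughout.
4. Preferably, if the sponsor accepts the burden, enter all elicited AEs with grade and relatedness as fields, and tabulate them regardless of causality with related events as a subset. Staff already ask about AEs at visits, so this adds modest data entry and no visits or procedures. The label and the AE exclusion in item 1 would then no longer be needed.
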